#### *Quantitative Methodology*

- i. *Chart Audits.* The study team will conduct virtual chart audits all four primary care practices (80 individuals per practice). The data will measure key behavioral health (i.e., depression), DMII process (i.e., self-management activities). The study team will conduct the audit, pre- intervention for a baseline, and 15 months post-intervention for follow-up. As noted earlier, chart audits are a secondary analysis of existing data; therefore, the study team will not recruit or seek consent from patients for the chart audits.
- ii. *Surveys.* The study team will administer two surveys during the study.

The first of which is a Practice Survey. One practice staff person (e.g., office manager, clinical lead) will complete this survey for each practice. The Practice Survey collects demographic data (e.g., ownership) and include items from the Change Process Capability Questionnaire to measure quality improvement strategies the practice uses. The survey will be administered online through RedCap.

The Practice Member Questionnaire will be administered online via Qualtrics to a select number of staff. We will ask the office manager for each practice to provide a list with employees' names, role and email addresses. The study team will use a stratified random process to select staff who will receive a survey. Staff who are selected will receive an email invitation from us to complete an anonymous online survey. We anticipate that there will be 10-15 practice members asked to complete this survey at each practice, but this will vary based on practice size and diversity of team roles. Due to COVID-19, the study team altered its initial approach, which would have taken place at an in-person all-staff meeting to collected baseline and follow-up data. For now, we are altering baseline data collection only.

For the initial submission, the study team is submitting for approval of the following qualitative and quantitative measures at baseline: the Pre-Site Visit Interview Guide, Site Visit Observation Guide, Practice Member Staff Interview, Patient Interview, Practice Survey, and Practice Member Questionnaire. As the study team refines the intervention, modifications to the IRB will be submitted.

For Study Modification #3, the study team re-submitted the Practice Survey. The revised version removes a number of descriptive items already available to the team (e.g., practice size, practice ownership), amended questions for the Oregon context (i.e., Patient Centered Primary Care Home (PCPCH) program), updated question phrasing, expanded answer choices (including “Don’t Know” and “Behavioral health team”) and incorporated three items about the use of an electronic health record system in primary care practices.

## **7. Data and Specimens**

### **a. Handling of Data and Specimens**

- i. *Primary Care Practices.* As noted earlier, team members will produce field notes from their observations. Neither protected health information nor identifiers will be recorded. Field notes will be prepared within 24 hours of the site visit’s end. Field notes will not include names, but refer to persons by role. Practices will be referred to using an identifying number (practice 1, 2). When reporting data in publications, reports, or grants data will remain de-identified.
- ii. *Practice Member Staff.* Interview data will be organized by participant code #. Interview recordings will be stored on the encrypted OHSU network. The interview will take about 60 minutes, and with permission, the interviews will audio-recorded. The audio recordings will be professionally transcribed, checked for accuracy and de- identified. As with the observations, the study will return for follow-up interviews.

For the Practice Survey, data will be collected and stored on the Oregon Clinical and Translation Research Institute (OCTRI) installation of REDCap, a highly secure and robust web-based research data collection and management system. Qualtrics, an online survey tool will be used for the Practice Member Questionnaire. Qualtrics is approved for use with OHSU-restricted information, including PHI. The study team included Qualtrics to anonymize survey data. Both surveys will be launched through the respective platforms, at baseline and follow-up.

- iii. *Patients.* Post-intervention (Year 2, quarter 3), the study team will conduct interviews with five patients, at each practice, that were exposed to the intervention to understand patients’ experiences with the practice changes that were implemented and the acceptability of those changes. Patient interviews will also consist of open-ended questions. All interviews will be audio-recorded and last approximately 60 minutes. The audio recordings will be professionally transcribed, checked for accuracy and de-identified.

### **b. Sharing of Results with Subjects**

Findings will be shared with participants if requested, at completion of the study. Results will be aggregated and will not include identifying information of the clinic site, staff/providers, or patients.

### **c. Data and Specimen Banking**

Data will not be used for future research planned at this time nor will specimens be collected.

## 8. Data Analysis

*Rapid Qualitative Assessment.* The qualitative team ([name], [name], [name]) will create baseline summaries for each intervention practice that include summarized practice characteristics, capacity data (e.g., Adaptive Reserve, CPCQ, HIT capacity) and preliminary insights from observation and interviews related to the delivery of psychosocial and DMII care. The aim is to rapidly summarize strengths, weakness and opportunities for change to inform the facilitator's work with practices.

*Hypothesis 1 Analyses—Assessing Feasibility and Acceptability and estimating cost of INTEGRATE-D.* Analyses for Aim 1 will be mixed methods. To evaluate the hypothesis that INTEGRATE-D is acceptable and feasible, the study team will use standard descriptive statistics to summarize each intervention practice's scores on the acceptability of intervention, intervention appropriateness and feasibility measures. Each measure includes four items, each on a 5-point Likert scale. The study team will create and summarize scales for each measure by averaging responses (where higher scores denote higher feasibility and acceptability) as is recommended.

The qualitative team will examine observation and interview data following the five-step process outlined by Miller and Crabtree (see Table 5, next page). The first step is to understand each practice as a separate case in its own context. To do so, the study team will analyze data as a group, reading field notes and listening to interviews from a practice to identify aspects of culture, team structure and operations, to identify how DMII care is delivered, how psychosocial care is integrated into DMII care process, and the factors influencing integration. The study team will compare pre- and post-intervention data to identify changes the practice made during INTEGRATE- D and why. Preliminary findings will be triangulated with what we learn in monthly phone calls with the key informants and survey data. The study team will also examine practice member experiences during the intervention (both good and bad), identify recommended improvements to the intervention, explore what tools and implementation strategies practices found most and least useful, and examine acceptability and feasibility. During this process, the qualitative team tags text with analytically relevant names (e.g., behavioral health screening) called “codes.” Once within- practice analyses are complete, we analyze data a second time to make comparisons across the practices; the study team will create matrices to display data across practices for comparative analyses as suggested by Miles and Huberman. The study team will seek additional data sources to confirm/disconfirm and refute findings.

Interview data will be used to assess the perceived costs / benefits of the INTEGRATE-D. These data will be analyzed and summarized using the procedures outlined above. Facilitator tracking data will be used to count the number of visits to each practice, the time spent during each visit (and between visits, if applicable) and the practice members who participated in QI meetings. The study team will use the average facilitator salary and estimates for practice member salaries (using national averages) to estimate the cost of the intervention. This will lay a foundation for a more thorough and systematic cost-effectiveness analysis planned for a subsequent R18.

*Hypotheses 2 and 3 Analyses—Assessing Change in Process of Care Measures.* The primary goal of hypothesis 2 is to evaluate whether the intervention had a higher number of process care metrics for DMII and depression as compared to control practices. For this hypothesis, our unit of analysis is at the patient level. To compare the effect of INTEGRATE-D on process outcome measures in the context of a cluster randomized design, the study team will implement Generalized Linear Mixed

Models (GLMMs). For our primary outcomes (which we treat as continuous variables), the study team will use a model that addresses the following design features of the study: (1) the study team will include a random intercept for practice to account for clustering of patients within practices; (2) the study team will perform an intent-to-treat analysis; (3) due to the pragmatic nature of the study, the patient sample will be an open cohort, with some patients remaining in the study for the entire duration and others joining the study when they come in during the study period. Because outcomes will be assessed multiple times, it may be possible that a patient shows up in both the pre and post period; thus, the study team will consider including random effects for the patient, if needed. Depending on the outcome type, the study team will take advantage of the flexibility of GLMM to model various forms of dependent variables, including the mixed effects versions of logistic regression (binary data), beta regression (percent data), Poisson regression (count data), and Gaussian regression (normally distributed data). For example, to assess changes in screening for PHQ-2 and PHQ-9, the study team will consider a logistic mixed effects model where we model the outcome of screened (yes versus no) as a function of an indicator for period (post vs. pre), indicator for intervention arm (intervention vs. control), and the interaction between period and intervention. If sample size allows and depending on imbalance between arms, we may consider adding a small set of unbalanced patient and practice-level confounders.

For the larger pragmatic hybrid implementation-effectiveness trial, the study team will extend this model to consider moderation analyses. Because we hypothesize that implementation support directly helps improve practice capacity for QI, the study team will evaluate whether practice capacity measured using Adaptive Reserve and CPCQ moderates the relationship between implementation support and distal and process of care outcomes. To do this, the study team will consider moderation analyses (e.g., heterogeneity of implementation support over time by practice capacity) by including interaction terms between study arm, time, and practice capacity in the models above.

For hypothesis 3, which compares the change in QI strategies over time between intervention and control practices, our unit of analysis is at the practice level, as only one member of the practice answers these questions. Given the low sample size (four practices each providing two surveys, resulting in eight data points), the study team will describe the change from pre to post in both groups using descriptive means, standard deviations and ranges for the overall CPCQ score and for each individual item. For the larger pragmatic hybrid implementation-effectiveness trial, we would consider a linear mixed effects model where the dependent variable would be the score (range = - 28 to +28) and fixed effects of period (post vs. pre), intervention arm (intervention vs. control) and the interaction between period and intervention plus covariates.

*Hypothesis 4 Analysis—Assessing Trends in Outcome Measures.* For hypothesis 4, the study team will utilize the GLMM modeling similar to what is proposed above. The study team will consider an analysis at both the patient and practice level. For patients that showed up in both pre and post periods, we are able to estimate their change in PHQ-9 and HbA1c values, and the study team will use linear mixed effect modeling to compare change across study groups. For practice-level analyses, the study team will take the average PHQ-9 and HbA1c values at both pre- and post- intervention periods for both arms and compare them descriptively. For the large pragmatic trial, the study team will extend the linear mixed model to account for a longer follow-up time and the multiple observations per patient over that follow-up time. The study team will consider different functional forms of time (e.g., linear splines) to model pre-post changes. Multiple observations in

such a longitudinal structure provides more rigor than just a pre-post analysis. The study team will also examine goodness of fit statistics and model fitting diagnostics to identify influential points and to evaluate alternative model specifications (e.g., Poisson mixed-effects models for PHQ-9).

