### 2. Objectives

The proposed study consists of two aims: 1) To refine INTEGRATE-D, an intervention that offers primary care practices implementation support to align type II diabetes mellitus care with American Diabetes Association recommendations for integrating medical and psychosocial care. 2) The study will pilot test INTEGRATE-D, recruiting and randomly selecting four primary care practices to an experimental condition (i.e., treatment and control group). The study team will use mixed methods to assess the acceptability, feasibility, and cost of implementing INTEGRATE-D and to understand the preliminary impact on DMII and behavioral health process and outcome measures. The study hypothesis are:

1. Practices receiving INTEGRATE-D will find it acceptable and feasible and worth the effort and cost.
2. Practices receiving INTEGRATE-D will meet a higher number of process-of-care metrics for DMII and depression (pre-post) as compared to control practices (primary hypothesis).
3. Intervention practices will report using more quality-improving strategies post-intervention than at baseline, compared to control practices.
4. Practices receiving INTEGRATE-D will demonstrate a positive trend (improvement in PHQ-9 and HbA1c scores (pre-post) as compared to control practices (secondary hypothesis).

The anticipated methodological approaches include, chart audits, observations, surveys, and semi-structured interviews. Practice member staff and patients will be recruited from the participating sites.

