### ***The INTEGRATE-D Intervention***

INTEGRATE-D was an implementation support intervention designed to help clinics align care with ADA recommendations. The intervention was initially comprised of 15-months of tailored external support that included three evidence-informed implementation support strategies: (1) Audit and feedback—assisting clinics in accessing actionable data reports to identify care gaps; (2) Skill-building resources—expert training on ADA-recommended care, DD, pragmatic screening and treatment strategies, and education in the medical aspects of type 2 diabetes targeted to BHCs; and (3) Facilitation—monthly, tailored support to help clinics identify and implement changes to align care with ADA recommendations utilizing Plan Do Study Act (PDSA) cycles and the Bodenheimer Building Blocks.

We modified INTEGRATE-D to accommodate strains due to COVID-19 and to align with what we learned from baseline assessments. Table 1 shows clinics received monthly facilitation remotely rather than in person. IC1 received 15 once monthly facilitation meetings; IC2 received 11 due to the delayed intervention start. Facilitation was tailored and included PDSA cycles that tested workflows to incorporate psychosocial screening; facilitators did not use audit and feedback data. We delivered two remote expert trainings to IC1. Trainings were recorded and shared with IC2.

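### The costing rule prices facilitation and QI-meeting time but not expert training, so the intervention cost is understated by an amount the documents do not determine (minor)

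*Protocol*

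**What the plan says.** Cost is a stated objective: Protocol section 2 says the team will "assess the acceptability, feasibility, and cost of implementing INTEGRATE-D".

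Protocol section 8, under Hypothesis 1, describes how. For quantities: "Facilitator tracking data will be used to count the number of visits to each practice, the time spent during each visit", with time between visits where applicable, "and the practice members who participated in QI meetings". For prices, the team will "use the average facilitator salary and estimates for practice member salaries (using national averages) to estimate the cost of the intervention". Separately, "Interview data will be used to assess the perceived costs / benefits of the INTEGRATE-D"; these data are analysed qualitatively. The paragraph closes with a limit on scope: "This will lay a foundation for a more thorough and systematic cost-effectiveness analysis planned for a subsequent R18".

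Protocol section 10.b promises practices expert training as well as practice support. The SAP's description of the intervention names expert training as part of one of three support strategies, distinct from facilitation, and reports that "We delivered two remote expert trainings to IC1", with recordings passed to IC2. SAP Table 1 gives training its own row and its own providers (a physician, a behavioral health clinician and a diabetes-distress expert). The practice facilitator has a different row. The SAP's measures and analysis sections contain no cost measure or cost analysis.

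**The concern.** The rule labels its result as the cost of the intervention, but it draws every quantity from the facilitator's log and every price from facilitator and practice-member salaries. A facilitator's log of visits and QI meetings has no evident reason to hold the hours that outside experts spent preparing and giving training, or the hours that staff spent attending it. No price is named for the trainers at all.

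If the rule is applied as written, the training component enters at zero. The pilot's cost figure would then be too low as an estimate for the whole intervention. The later cost-effectiveness work, for which the protocol offers this figure as a foundation, would start from a base that lacks one of the two components listed as delivered in SAP Table 1.

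**Working it through.** Neither document states a cost, an hourly rate or a number of hours, so there is no figure to reproduce. The check has two parts: which resources the rule covers, and a person-hour illustration of what it leaves out.

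**Coverage**

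| Resource | Where described | In the costing rule? |
|---|---|---|
| Facilitator visits, time in and between visits | Protocol 8 | Yes |
| Practice members at QI meetings | Protocol 8 | Yes |
| Trainer delivery and preparation | SAP Table 1 (training as a component) | No quantity, no price |
| Staff time attending training | SAP Table 1 (training for clinical teams) | Not counted; the only attendance named is at QI meetings |

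Omitted hours cannot be negative. With the salary inputs held fixed, the total can only be too low.

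**Inputs from the SAP**
- Facilitation meetings: 15 at IC1 and 11 at IC2.
- Live trainings: 2, at IC1 only.
- Trainers: two at the first training (physician and diabetes-distress expert) and one at the second (clinical psychologist), so 2 + 1 = 3 trainer-sessions.
- Audience: all clinical roles at the first training, behavioral health clinicians at the second.

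**Assumed inputs (not in the documents)**
- Each facilitation meeting: 1 hour, 5 staff, 2 facilitator hours including time between visits.
- Each training: 1 to 2 hours, with 2 to 6 hours of preparation per trainer-session.
- Attendance: 10 to 15 at the first training, 1 to 3 at the second.
- IC2 training time: zero, because it had recordings only.

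**Counted hours** = meetings × (staff × 1 h + 2 h)
- IC1: 15 × (5 + 2) = 105 h
- IC2: 11 × (5 + 2) = 77 h
- Both: 105 + 77 = 182 h

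**Omitted hours** = length × (attendees at first + attendees at second) + 3 × (length + preparation)
- Low: 1 × (10 + 1) + 3 × (1 + 2) = 11 + 9 = 20 h
- High: 2 × (15 + 3) + 3 × (2 + 6) = 36 + 24 = 60 h

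**Omitted share** = omitted / (omitted + counted)
- IC1: 20/125 = 16%; 60/165 = 36%
- Both clinics: 20/202 = 10%; 60/242 = 25%

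**Wider sensitivity range, both clinics.** This keeps the 26 meetings and 2 trainings. It assumes meetings of 0.5 to 1 h with 2 to 5 staff plus the facilitator, 0 to 1 h between visits, trainings of 1 to 2 h with 1 to 2 trainers and 4 to 12 attendees each, and 0 to 8 h preparation per training.
- Smallest share: counted 26 × (1 × 6 + 1) = 182 h; omitted 2 × (1 × 5 + 0) = 10 h; 10/192 = 5%
- Largest share: counted 26 × (0.5 × 3 + 0) = 39 h; omitted 2 × (2 × 14 + 8) = 72 h; 72/111 = 65%

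These are shares of person-hours. A share of money depends on wages, which the documents do not give.

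**The case against.** The strongest reply is that this is a short description of a preliminary estimate, not a closed list. The protocol never says that only these hours count and never excludes training. Practice-member salaries are already in the method and could be applied to training attendance. A fuller analysis is deferred to a later study, and no test, threshold or decision depends on the salary total.

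The limits on importance stand. The rule is still incomplete: it identifies attendance only at QI meetings, has no price for trainers, and does not label its result as partial. That training is free to practices is no answer either. Facilitation is also free to them, yet the facilitator's salary is counted, and staff time at training is a cost to the practice in any case.

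A reader might infer more than the documents support:

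- **That half or more of the cost is missing.** Shares of that size need generous assumptions. The SAP supports 3 trainer-sessions, not three trainers at both sessions, and the second training was aimed at behavioral health clinicians. The SAP's Data Collection section reports 17 team members exposed to the intervention, so even 10 to 15 attendees at IC1 may be high.
- **That data-report support is another uncosted input.** Audit and feedback was planned and the protocol promises tailored reports. But the SAP says facilitators did not use those data, and SAP Table 1 lists only training and facilitation.
- **That facilitator preparation is missed, or that the clinic difference is hidden.** The rule already includes facilitator time between visits and counts by practice. The SAP openly reports live training at IC1, recordings at IC2, and 15 against 11 meetings.
- **That the conclusion on hypothesis 1 is distorted.** Whether the intervention was worth its cost is addressed mainly by interviews on perceived costs and benefits.
- **That the SAP contains a biased cost result.** It contains no cost analysis. That is a separate gap; the point here concerns the protocol's rule.

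**Conclusion.** The point holds as a minor one. The costing rule omits expert training, both trainer time and staff attendance, and so understates the cost of the intervention. The direction follows from the omission alone. The size does not follow from the documents: 16% to 36% of person-hours at IC1 and 10% to 25% across both clinics rest on assumed meeting lengths, attendance and preparation, and other plausible inputs move the two-clinic figure anywhere from about 5% to 65%. None of these ranges should be quoted as a finding about the trial. The rule is better described as an incomplete resource list than as a deliberate exclusion.

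**What to change.** A cheap improvement. Add to the costing paragraph in Protocol section 8, and to any cost table, a separate training line by clinic with:

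- trainer delivery hours and trainer preparation hours;
- staff hours attending training;
- national average salaries for the relevant roles as prices, in line with the method already chosen for practice members.

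For IC2, state that only recordings were provided and that their use is unknown, so that an empty cell is not read as a known zero. If the hours cannot be recovered, keep the present calculation and label it as facilitation cost only.

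The cost is a few extra time entries and one more table line. The downside is that the trainings are past (March and May 2021 at IC1), so hours must come from calendars or recall and will be approximate.
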